4.2 BACKGROUND ON SAR407899

SAR407899 is an inhibitor of Rho kinase (ROCK), a broadly expressed serine/threonine protein kinase.

SAR407899 has already been studied in healthy adult volunteers, healthy elderly subjects, patients with chronic kidney disease (CKD) and patients with erectile dysfunction. Although SAR407899 was generally well-tolerated, dose-related symptomatic orthostatic hypotension occurred in some subjects, primarily after administration of the first dose, and particularly in patients who had renal dysfunction and who were treated with concomitant anti-hypertensive drugs. Orthostatic hypotension is considered to be a mechanism-related effect and will be mitigated in the current study by using an individual dose titration approach. In healthy young subjects, a few cases of serum creatinine increase >30% were observed however the values remain within normal range. This effect was not observed in elderly subjects or in patients with CKD.

4.3 RATIONALE FOR THE STUDY

This study will evaluate SAR407899 compared with placebo in a population of patients with microvascular angina and/or persistent angina despite angiographically successful PCI (typical or atypical symptoms of angina pectoris), non-obstructive (<50% stenosis) coronary arteries on angiogram or intermediate stenosis with FFR >0.80 or iFR >0.89, and microvascular dysfunction documented by a global CFR <2.0 measured by PET. Angiographically successful balloon angioplasty with a reduction of a minimum stenosis diameter to <50% or for coronary stents a minimum diameter stenosis of <10%, with a final TIMI flow Grade 3 (visually assessed by angiography) without side branch loss, flow-limiting dissection, distal embolization, or angiographic thrombus.

This study will assess whether SAR407899 improves PET scan global CFR (25) before and after administration of a pharmacologic stressor (ie, vasodilator). Low CFR is considered as a hallmark of microvascular dysfunction. An improvement in CFR observed after interventions in this patient population would suggest an improvement in the underlying causal vascular biological abnormalities. Assessment of patient-reported outcome using the Seattle Angina Questionnaire physical limitation scale (SAQ-PL) due to its sensitivity will be used as secondary endpoint.

Change in angina episodes and short-acting nitrate intakes will be collected in the patient's diary.

4.4 DESIGN RATIONALE AND RISK ASSESSMENT

- This study will be placebo-controlled as no treatment is currently approved in the population with microvascular angina and/or persistent stable angina despite angiographically successful PCI. The drug will be tested on top of standard treatments for angina excluding nitrates (except short-acting nitrates) and PDE 5 inhibitors that should be discontinued at least one week before baseline PET assessment and not used during the study in order to avoid masking the effects of SAR407899 while increasing the risk of orthostatic hypotension.
- Beta-blockers act directly on the heart to reduce heart rate, contractility, AV conduction and ectopic activity. Additionally, they may increase perfusion of ischemic areas by

prolonging the diastole and increasing vascular resistance in non-ischemic areas this is why beta-blockers are currently first-line anti-anginal therapy in stable CAD patients without contraindications according to ESC 2013 guidelines on stable CAD (26). Hence, beta-blockers should be kept at the same dose, as it could potentially impact the assessment of efficacy.

- SAR407899 will be administered in the morning and at bedtime. As no relevant food-effect was demonstrated, dose may be taken with or without food as per preference of the patient. Twice a day (BID) regimen has been chosen in order to minimize peak concentration effects while maintaining sufficient trough levels.
- Decrease in BP (hypotension, orthostatic dysregulation) is considered as a mechanism-related effect and will be mitigated by using a dose titration approach.

[REDACTED]

A safety review will be performed by the DMC when 19 patients will have completed the first week of treatment. The DMC will review the clinical safety data including AESIs. During the safety evaluation of the first 19 enrolled patients, these patients will continue to receive IMPs as per the titration schedule described above and enrolment will continue.

- If patient does not tolerate a dose level due to hypotension, symptomatic orthostatic hypotension with SBP decrease ≥ 20 mmHg, at Minute 3 or Minute 5 after changing position from seated to standing, the investigator will decrease the dose level of the investigational product to the previous tolerated dose level for the remaining duration of the study.
- Overall, the exposure to the study drug should last for 4 weeks in total (3 weeks for the titration phase and 1 week for the maintenance phase) for all patients. Patients will be followed one week after the end of the study treatment to collect any potential AEs during the washout period.
- Serum creatinine will be monitored. Creatinine is filtered in glomerulus and also partly eliminated in urine via an active secretion mediated by organic cation transporter-2 (OCT2). These observed increases in adults could then possibly be explained by inhibition of its active secretion by SAR407899 which is a weak in vitro OCT2 inhibitor. Serum cystatin C, which is filtered in glomerulus but not subject to tubular secretion, will be measured in parallel to serum creatinine to assess glomerular filtration rate.

Specific parameters rationale

Primary endpoint:

- **Coronary flow reserve (CFR)**, represents blood flow to the myocardium; the critical factor in angina. It is the endpoint with the most abundant clinical data in MVA patients. CFR is the ratio of the maximal myocardial blood flow (MBF) after a hyperemic stimulus (such as intravenous adenosine injection) to baseline resting blood flow. In patients with

normal endothelial function, adenosine increases MBF by a factor of 2.5 or more while in patients with endothelial dysfunction the increase is less than 2.0 (27).

Secondary endpoints:

- **The Seattle Angina Questionnaire (SAQ) (28)** was used in pilot MVA studies. It is currently used in clinical trials in MVA populations for ranolazine and thus provided a basis for statistical calculations. The SAQ is a self-report instrument with 19 items designed to quantify the physical and emotional effects of coronary artery disease. The questionnaire has a 4-week recall period. It yields five dimensions, each scored separately: physical limitation, angina stability, angina frequency, treatment satisfaction, and disease perception. A SAQ-7 summary score can also be derived using 7 items from the physical limitation, angina frequency and disease perception domains. The physical limitation (SAQ-PL) dimension is the most relevant for defining treatment benefit in this trial and was thus specified as a secondary objective. The SAQ-PL dimension measures how common daily activities representing low, medium, and high exertional requirements are limited by angina (9 items). It is scored by assigning each response an ordinal value, beginning with 1 for the response that implies the lowest level of functioning, and summing across the 9 items. The score is then transformed to 0-100 range by subtracting the lowest possible scale score, dividing by the range of the scale and multiplying by 100. The possible range of scores is therefore 0 to 100, with higher scores better. A change of 10 points is considered to be clinically important.
- **Safety** will be assessed during the whole study on adverse events with a special focus on BP, laboratory data and renal function.

Exploratory endpoints:

Assessment of angina episodes with or without short-acting nitrate intakes

Angina episodes and short-acting nitrate intakes collected by the patients in a diary will be measured. This will allow assessing the number of angina episodes (and their severity).

Assessment of other dimensions of the SAQ and SAQ-7 score (29)

The SAQ yields five dimensions, each scored separately: physical limitation, angina stability, angina frequency, treatment satisfaction, and disease perception. All the dimensions except SAQ-PL will be assessed.

The SAQ-7 summary score can also be derived using 7 items from the physical limitation, angina frequency and disease perception domains.

Assessment of patient's perceptions of treatment and symptoms

The patient qualitative self-assessment aims to better understand the patient's views on their treatment and symptoms at baseline and at the end of the study. Three questions assessing the patient's perception will be asked and a free-text box will be provided for patients to give qualitative answers. This assessment should take between 5-10 minutes, and the text will later be

analyzed using qualitative data analysis software to perform content analysis using text mining. The patient will be asked to complete these three questions. The questions are:

- Day 1 and at the end of treatment visit/permanent treatment discontinuation or Day 29: “Please think back over the **past week**. In your own words, please describe the symptoms you have experienced because of your **angina without obstructive coronary artery disease**.”
- End of treatment visit/permanent treatment discontinuation or Day 29 only: “Please think about the study you have been part of. In your own words, please list the pros and cons of study treatment”.
- End of treatment visit/permanent treatment discontinuation or Day 29 only: “Please give your overall thoughts on the study treatment you have received as part of this study”.

[REDACTED]

[REDACTED]

[REDACTED]

5 STUDY OBJECTIVES

5.1 PRIMARY

- Assess the effects of SAR407899 on coronary vasomotor function using CFR in patients with microvascular angina and/or persistent stable angina despite angiographically successful PCI.

5.2 SECONDARY

- Assess the effects of SAR407899 in patients with microvascular angina and/or persistent stable angina despite angiographically successful PCI using SAQ-PL.
- Assess the safety of SAR407899 in patients with microvascular angina and/or persistent stable angina despite angiographically successful PCI with a focus on identified risks such as hypotension and orthostatic hypotension.
- Assess SAR407899 plasma concentrations in microvascular angina patients and/or persistent stable angina despite angiographically successful PCI.

6 STUDY DESIGN

6.1 DESCRIPTION OF THE STUDY

A Phase 2a, multi-center, randomized with 1:1 ratio, double-blind, placebo-controlled parallel group study with weekly titration up to maintenance dose, based on individual patient tolerability, particularly symptomatic or asymptomatic BP decreases.

6.2 DURATION OF STUDY PARTICIPATION

6.2.1 Duration of study participation for each patient

- Screening: up to 4 weeks before the first dosing (Day -28 to Day -1) and up to 6 weeks in patients diagnosed with MVA and stable angina without previous PCI who did not have a coronary artery angiography or CCTA in the previous 24 months but between 24 months and 5 years prior to screening and requiring CCTA in this screening period.
- Titration phase: 3 weeks.
- Maintenance phase: 1 week.
- Total duration of treatment: 4 weeks (including titration).
- Follow-up: 1 week.
- Total study duration: 9 weeks (± 2 days) and up to 11 weeks (± 2 days) in patients requiring CCTA in screening period.

6.2.2 Determination of end of clinical trial (all patients)

The end of the clinical trial is defined as the day when the last patient completes her/his last visit planned in the protocol.

6.3 INTERIM ANALYSIS

A safety review with a DMC meeting will start as soon as the first 19 patients will have been randomized and have finished the first week of treatment. Additional analyses for safety may be performed in this study.

Refer to [Section 11.5](#) and to [Section 6.4.1](#) for details on interim analyses.

6.4 STUDY COMMITTEES

6.4.1 Data Monitoring Committee

A Data Monitoring Committee (DMC) will be charged with monitoring the safety of the patients participating in this clinical trial. This committee is comprised of externally-based individuals with expertise in the diseases under study, biostatistics, or clinical research. The DMC will review all serious adverse events (SAEs), death, and adverse events of special interest (AESIs), in due time. The DMC will give appropriate recommendations to the Sponsor on safety aspects during the conduct of the study, if needed. The DMC is justified by the early stage of development of SAR407899 that has not gathered safety information in patients with microvascular angina or persistent angina despite angiographically successful PCI and the identified risk of hypotension. The DMC responsibilities and the data review processes are fully described in the DMC charter that will be developed prior to study start.

In the above capacities, the DMC is advisory to the Sponsor. The Sponsor is responsible for promptly reviewing and for taking into account in a timely manner the recommendations of the DMC in terms of trial continuation with or without alterations or of potential trial termination.

Following DMC review of the safety data (of the first 19 patients who will have completed first week after randomization) and their recommendations, the Sponsor may have to adjust titration schedules and dosing regimen.

7 SELECTION OF PATIENTS

7.1 INCLUSION CRITERIA

- I 01. MVA and/or persistent stable angina despite angiographically successful PCI male or female patients with:
- A) Male and female patients not at childbearing potential ≥ 18 year-old or legal age of majority.
 - B) Female patient if she has undergone sterilization at least 3 months earlier or is postmenopausal.
 - Post-menopausal status is defined by having no menses for 12 months without an alternative medical cause,
 - In females not treated with HRT, menopausal status is confirmed by a high follicle stimulating hormone (FSH) level greater than 40 IU/L,
 - In females on HRT and whose menopausal status is in doubt (ie, in women aged less than 45 years), a highly effective contraception methods will be required. Contraception should be used during the whole study and for at least seven days corresponding to time needed to eliminate study treatment.
 - C) Symptomatic stable angina pectoris (typical or atypical symptoms with an average of at least bi-weekly episodes over the past month).
 - D) Patients with non-obstructive (<50% stenosis) coronary arteries or intermediate stenosis (between 50 and 70%) should have FFR >0.80 or iFR >0.89 on angiogram, documented within the previous 24 months*. In patients with stenting, a minimum diameter stenosis of <10% is required.
or
Coronary computed tomography angiography with finding of non-obstructive coronary arteries within the past 24 months* in patients without previous PCI.

*Note: in cases of clinically suspected progression of atherosclerosis as per the Investigator, a more contemporary (i.e., 6 months) evidence should be provided.
or
CCTA performed during screening period, with finding of non-obstructive coronary arteries, in patients diagnosed with MVA and stable angina without previous PCI who did not have a coronary angiogram or CCTA in the previous 24 months but between 24 months to 5 years .
 - E) Baseline global CFR (measured during the study) assessed by ^{13}N -ammonia or $^{82}\text{Rubidium}$ PET scan <2.0.
- I 02. Signed written informed consent.
- I 03. Not under any administrative or legal supervision.

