- c Concomitant medication (if those are not allowed during the study, see exclusion criterion 3 in [Section 7.2.1](#)) needs to be stopped 1 week before baseline CFR assessed by PET scan and during the whole study.
- d Capsules in the morning and at bedtime. If PET assessment on Day 29 no administration at bedtime. If PET assessment delayed, last IMP administration should be done in the morning of the PET assessment.
- e Vital signs: BP & heart rate measurements including search of hypotension (orthostatic or not).
- f Before morning administration, vital signs should be assessed by the investigator or designee except on Day 1 which requires before morning administration, at T1H and T3H. For any safety reasons additional physical examination, vital signs, ECG may be performed at the investigator's discretion.
- g At Day 1 & Day 29 PET assessments, continuous monitoring of heart rate, BP and ECG should be performed throughout the stressor infusion.
- h Restriction rules for CFR assessed by vasodilator stress PET scan (detailed in [Section 10.1.2](#) and [Section 10.1.4](#)) to follow.
- i On Day 1 (or, if not otherwise possible, up to 14 days prior to Day 1) CFR assessed by vasodilator stress PET scan should be performed before the IMP administration. On Day 29 or up to 2 days after (if not otherwise possible) CFR assessed by vasodilator stress PET scan should be performed approximately 1 to 2 hours after morning IMP intake. Prior to baseline PET assessment (on day 1 or up to 14 days prior to day 1), the eligibility criteria must be carefully reviewed (including review of the screening labs), and if the patient no longer qualifies for the study, then he/she should not undergo the PET assessment.
- j To be completed before any other assessment and without any help.

- k Health care resources will include number of out-patients visits by type physician (specialists, general practitioner, other) and impact on working status.
- l Two PK samplings on Day 1 (1h and 3 h post-dose), one PK sampling (pre-dose) at Day 8, Day 15 and Day 22, two PK samplings on Day 29 (pre-dose and 1-3 hours post-dose). The patient will have to come at the site without having taken his morning dose of IMP if the visit occurs in the morning.
- m Only in post-menopausal female patient not receiving hormone replacement therapy.
- n Except hematology.
- o To assign patient number.
- p To obtain the treatment number after specifying the chosen titration.

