9.1.4 Assessment methods and activity parameters

9.1.4.1 ¹³N-ammonia or ⁸²Rubidium PET scan

Coronary Flow Reserve is assessed by PET scan in the morning at baseline (Day 1 or up to 14 days prior to first day of study drug administration and up to 4 weeks before in patients diagnosed with MVA and stable angina without previous PCI and whose coronary angiogram or CCTA was not performed in the previous 24 months but between 24 months to 5 years) and end of treatment Day 29 visit (or up to Day 31), approximately one or two hours after last IMP intake.

PET scan CFR procedure is described hereafter. Details on the procedure are contained in the imaging acquisition guidelines (IAG).

9.1.4.1.1 Positron emission tomography (PET):

Regional and global MBF will be assessed using PET imaging in accordance with the study-specific acquisition protocol (see IAG). PET scans will be performed using a whole body PET scanner.

Anti-hypertensives, beta-blockers and calcium channel blockers will be withheld 24 hours prior to

PET scan. Patients will be allowed to continue using sublingual nitroglycerin as needed. Studies will be performed after 4 hours of fasting and 24 hours of abstinence from caffeine-containing products. The PET scan will take approximately 2.5 hours, including patient preparation.

Myocardial blood flow (MBF) will be measured at rest and during maximal hyperemia using adenosine or regadenoson infusion, and using ^{13}N -ammonia or ^{82}Rb as the flow tracer. After transmission imaging and beginning with the intravenous (IV) administration of the flow tracer, list mode images are acquired. Then, patients will undergo a standard infusion of adenosine or bolus injection regadenoson. At peak hyperemia, a second dose of the flow tracer will be injected IV, and images recorded in the same manner. The heart rate, BP, and 12-lead ECG will be recorded at baseline and throughout the infusion of adenosine or regadenoson, and at recovery. All PET scans will be done for research (non-clinical) purposes only. For safety reasons, all PET scans will be reviewed at the sites by site investigators for clinically important findings. No reports or analyses will be provided to sites from the PET core laboratory and studies will not be assessed in real-time.

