9.1.4.5 Coronary computed tomography angiography

A CCTA will be performed only in patients without previous PCI and whose coronary angiogram or CCTA was not performed in the previous 24 months but between 24 months to 5 years in whom screening PET scan results and CFR < 2.0 qualify for the study. This additional investigation will be performed according to common practice.

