9.2.3 Laboratory safety variables

The clinical laboratory data are collected in accordance with the study schedule ([Section 1.3](#) and [Section 1.4](#)) and consist of:

- Blood count: red blood cell count (RBC - with morphology if blood cell count is abnormal), hematocrit (Hct), hemoglobin (Hb), white blood cell count (WBC) with differential (neutrophils, eosinophils, basophils, monocytes and lymphocytes), platelets.
- Serum Biochemistry:
 - Plasma/serum electrolytes: glucose, sodium, potassium, chloride, calcium, bicarbonate, BUN, creatinine (with estimated glomerular filtration rate), uric acid, total protein, albumin, creatine phosphokinase (CPK), LDH and cystatin C,
 - Lipid profile: total cholesterol, HDL cholesterol, LDL cholesterol, triglycerides,
 - Liver function: AST, ALT, alkaline phosphatases, gamma-glutamyl transferase (GGT), total and conjugated bilirubin.
- Urinalysis: dipstick for proteins, glucose, blood, leucocytes, ketone bodies, pH, bilirubin, urobilinogen, nitrite, specific gravity. If positivity of this test, microscopic analysis has to be considered.

Clinical laboratory values will be analyzed after conversion into standard international units. International units will be used in all listings and tables.

Decision trees for the management of some laboratory abnormalities are provided in [Appendix A](#).

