10 STUDY PROCEDURES

10.1 VISIT SCHEDULE

10.1.1 Visit 0: Screening visit

The screening visit has to be performed 4 weeks to one day before scheduled (first) dosing (Day 1) and up to 6 weeks in patients before scheduled (first) dosing with CCTA during screening.

Informed Consent

Information on the study will be given to and discussed with the patient. The patient will sign the informed consent for the current trial before any procedure. When the consent has been obtained, full identification of patient and personal physician will be recorded for the Investigator's record, and a subject number will be assigned as described in [Section 8.3](#).

Also the informed consents have to be obtained for the optional DNA banking and future use of samples for possible later further analyses.

Collection of adverse events has to be started from the time of signing informed consent. The patient has to be registered with the IVRS/IWRS.

After the informed consent has been signed, the following measurements have to be performed:

- Call IVRS/IWRS to assign patient number.
- Demographic information.
- Collection of prior/concomitant medications.
- Begin AEs reporting.
- Medical/surgical history.
- Data of previous (if done 24 months prior to screening) coronary artery angiography or CCTA.
- Data of previous (if done between 24 months and 5 years prior to screening) coronary artery angiography or CCTA.
- Data of previous (if done 24 months prior to screening) CFR assessment whatever the method.
- Assessment of inclusion and exclusion criteria.
- Physical examination (including smoking habits).
- Body weight and height.
- Vital signs, resting 12 lead-ECG.

Patients who do not meet inclusion criteria and/or met at least one exclusion criterion will be considered a screening failure and will not perform the following measurements:

- Blood sampling for hematology, biochemistry and plasma FSH (For post-menopausal female patients not treated with HRT).
- Blood sampling for renal function (blood creatinine and cystatin C).
- Collection of urine for urinalysis.
- A patient diary will be dispensed to the eligible patients in order to record their angina episodes and the short-acting nitrates intakes.

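### The visible protocol schedules no pregnancy test before the baseline PET, any screening CCTA or the first dose for unsterilized women under 45 on HRT, whose menopausal status it treats as uncertain

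*Protocol*

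**What the plan says.** I01 A in Section 7.1 admits only patients without childbearing potential. I01 B gives women two routes: sterilization at least 3 months earlier, or postmenopausal status. On the second route, "Post-menopausal status is defined by having no menses for 12 months without an alternative medical cause". Women not on HRT must also have an FSH above 40 IU/L. For women on HRT the text differs: "In females on HRT and whose menopausal status is in doubt (ie, in women aged less than 45 years), a highly effective contraception methods" must be used, for the whole study and at least seven days more. The synopsis repeats the clause.

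FSH sampling follows the same split. Footnote m of both study flow charts (Sections 1.3.1 and 1.3.2) reads "Only in post-menopausal female patient not receiving hormone replacement therapy". Section 10.1.1 lists "plasma FSH (For post-menopausal female patients not treated with HRT" among the screening samples.

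The only urine test described is in Section 9.2.3: "Urinalysis: dipstick for proteins, glucose, blood, leucocytes, ketone bodies, pH, bilirubin, urobilinogen, nitrite, specific gravity". Before the baseline PET, footnote i in Section 1.3.1 says "the eligibility criteria must be carefully reviewed (including review of the screening labs), and if the patient no longer qualifies for the study", the scan should not go ahead.

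Pregnancy appears as a reason for stopping study drug (Sections 10.3 and 10.3.2) and as an adverse event of special interest (Section 10.4.1.3). E27 concerns breast feeding only.

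**The concern.** The protocol itself says that menopause is uncertain in this subgroup, and it requires contraception for that reason. Contraception lowers the chance of a new pregnancy but does not reveal one already present. If the visible protocol is followed to the letter, no scheduled procedure would find such a pregnancy before the radiotracer, a CCTA where one is needed, and up to 31 days of dosing (Section 8.1.1). Section 9.1.4.1.2 acknowledges radiation risk from the PET. The stopping rule and the special-interest reporting act only once a pregnancy is known.

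This is a participant-safety point. It does not touch power, type I error or the analysis.

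**Working it through.** The plan states no figure to reproduce. The check is a search of the schedule, followed by the timing and the test count.

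**1. Is a test scheduled anywhere?**

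- Study flow charts (1.3.1, 1.3.2), Day 1 charts (1.4.1, 1.4.2), Day 29 chart (1.5): no pregnancy test.
- Laboratory list (9.2.3): biochemistry and dipstick, no pregnancy test.
- Blood-volume table (9.6): a line for FSH, none for a pregnancy test.
- Visit lists (10.1.1 to 10.1.5): none.

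Visits 0 to 6 make seven numbered visits. Urinalysis is done at three of them (screening, Day 1, Day 29) and pregnancy testing at none. An early PET is a separate attendance in Section 1.4.2, with no urine collected that day. The pre-PET review relies on screening laboratory results, which contain no pregnancy test.

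**2. What does the contraception duty already cover?** Section 6.2.1 counts screening as part of the study: 4 + 4 + 1 = 9 weeks, or 6 + 4 + 1 = 11 weeks on the CCTA route. On that reading the duty starts at screening. What remains is a pregnancy conceived before screening and not recognised, or one after contraceptive failure, in a woman with a year of unexplained amenorrhoea.

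**3. When would a test have to be done?**

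- PET on Day 1: urine at -3H, PET at -2H30, dose at 0H. One test on the existing urine covers scan and dose.
- Early PET, standard route: screening is Day -28 to Day -1 and PET Day -14 to Day -1. Screening urine may be up to 28 - 1 = 27 days old at the scan, so a screening test is badly timed. The first dose follows the PET by 1 to 14 days, so a second test is needed.
- CCTA route: PET up to 28 days before Day 1. The CCTA follows a qualifying PET and its result is needed before Day 1, so the gap from PET to CCTA is 0 to at most 27 days.

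**4. Tests per woman who goes on to dosing**

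| Route | Tests | Extra urine samples |
|---|---|---|
| PET on Day 1 | 1 | 0 |
| Early PET, no CCTA | 2 | 1 |
| CCTA on the PET day | 2 | 1 |
| CCTA on a later day | 3 | 2 |

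The count has to be per woman scanned. The PET and the proposed tests come before randomization, so a woman whose CFR is not below 2.0 is also scanned and tested. She needs only the PET-day test, because no CCTA or dose follows.

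**5. Exposure to active drug.** Allocation is 1:1, so about half of any such women who are randomized would receive SAR407899. The scans affect all of them.

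**The case against.** The strongest reply is that several layers already deal with this. I01 A excludes childbearing potential, and the HRT clause adds to the 12-month rule without waiving it. Contraception applies from screening. Eligibility is reviewed before the PET and again on Day 1. E04 allows exclusion for gynecologic disease and E17 for contraindications to either scan. Section 8.1.2 requires tracers and stressors to be used as labelled. Section 9.1.4.5 says of CCTA, "This additional investigation will be performed according to common practice". Section 9.1.4.1 adds, "Details on the procedure are contained in the imaging acquisition guidelines (IAG", and that document is not available to us.

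Most of this stands, and it makes the risk very low. It does not close the gap. These safeguards rest on investigator judgement or on unseen documents, and none visibly schedules a test. E17, the labelling and common practice for CCTA concern the imaging and do not cover the first dose of study drug.

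Three stronger readings are tempting, and the documents do not support them:

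- A reader might infer that the missing FSH is the error. The protocol deliberately substitutes contraception for FSH in women on HRT.
- A reader might infer from E27 that known pregnancy is allowed. A woman recognised as pregnant would fail I01, so adding the word to E27 would only clarify.
- A reader might infer that sites will scan and dose without testing. Imaging guidelines, local amendments or site practice may require a test, so only the absence from the visible protocol can be asserted.

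**Conclusion.** The point holds as a small, optional safety improvement. For unsterilized women under 45 on HRT, the visible protocol schedules no pregnancy test before the baseline PET, any screening CCTA or the first dose. The residual risk is confined to an unrecognised pregnancy from before screening or after contraceptive failure.

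The documents do not say how many of the 78 planned patients would fall in this subgroup. It may be none, and any percentage would be guesswork. The conclusion rests on two assumptions: that the contraception duty begins with screening, as the study-duration arithmetic implies, and that no unseen document already requires a test.

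SAP Section 1.2 reports that the trial ended early with 10 patients randomized. The practical value therefore lies in a restart or in a later protocol that reuses the clause.

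**What to change.** Keep the HRT clause and its contraception duty. Add to I01 B and to the matching synopsis text, for unsterilized women under 45 on HRT only:

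*A negative urine pregnancy test is required (a) on the day of the baseline PET before the radiotracer, using the -3H urine if the PET is on Day 1; (b) before the CCTA if it takes place on a later day than the PET; and (c) on Day 1 before the first dose if the PET was done earlier.*

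Update the two study flow charts, the two Day 1 charts, the laboratory list in Section 9.2.3 and the visit lists in Sections 10.1.1 and 10.1.2 to match.

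The cost is 1 to 3 urine tests and 0 to 2 extra samples per affected woman who goes on to dosing, and one test for a woman scanned but not enrolled. A positive result would need repeating and could delay a scan, and a very early pregnancy could still be missed. Under Section 15 the change needs an amendment with IRB/IEC approval and, if judged substantial, health-authority approval. It may also need a revised consent form with re-signature. It is best combined with another amendment or made when the clause is next used.
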